**Table 1. Schedule of Assessments: Part 1**

Visit Identifier	Screening	Treatment Period Cycle 1					Treatment Period (each 28 Day Cycle)		EOT/Visit	FU Visit	LTFU	Notes/Protocol Section
		Day 1	Day 4	Day 8	Day 15	Day 22	Cycles 2-6 Day 1	Cycle 7 Onwards Day 1				
Visit Window	Day-28 to Day-1		-1/+3 D	-1/+3 D	±3D	±3D	±3D	±3D	14 Dpost- final dose	28 to 35 days post- final dose	± 14D	
Phannacokinetics and Immunogenicity Assessments												
Blood sample for PK		X	X	X			X (C2, 4, 6)	X* (C10, 16, etc.)	X			Predose, 24, and 48 hrs postdose on C1D1. Predose and 24 hon C1D4. Collect predose on C1D8, and Day 1 of C2, 4, 6, then at D1 of eveiy sixth cycle starting from C10(ie, C10D1, C16D1, etc.). If CRS is suspected, additional PK samples should be collected if not ah-eady scheduled.  CCI
Blood sample for ADAs and Nabs		X					X (C2, 4, 6)	X (C10, 16, etc.)	X			Predose on C1D1, C2D1, C4D1, C6D1, and eve,y sixth cycle sta,tng C10(ie, C10D1, C16D1, etc). If AE possibly related to ADA occurs, additional samples for ADA and PK should be collected if not scheduled. See Section 8.7.

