**Table 2. Study Schedule of Assessments: Part 2**

Visit Identifier	Screening	Treatment Period Cycle 1					Treatment Period (each 28 Day cycle)			EOT Visit	FU Visit	LTFU	Notes/Protocol Section
		Day 1	Day 4	Day 8	Day 15	Day 22	Cycle2 Day1	Cycles 3-6 Day1	Cycle7 Onwards Day1				
Visit Window	Day-28 to Day-1		-1/+3 D	-1/+3 D	±3 D	±3 D	±3D	±3D	±3D	14D post- final dose	28 to35 days post-final dose	± 14D	
Phannacokinetics and Immunogenicity Assessments													
Blood sample for PK		X	X	X			X	X (C4 and C6)	X* (C8, 10, 13, etc.)	X			
Predose, 24 and 48 hrs postdose on C1D1. Predose and 24 hon C1D4 and C2D1. If no hospitalization required on C2D1 for Part 2B and Pait 2C, the 24 h postdose w-ill not be required.
 
Collect predose on C1D8 and on DI ofC2, 4, 6, 8, then at Day 1 of eve1y third cycle starting C10 (ie, C1OD1, C13D1, etc).
 
In the event of suspected CRS, unexpected or serious AE, or AE leading to discontinuation of study intervention, additional PK samples should be collected if not already scheduled.
 
CCI

Blood sample for ADAs and NAbs		X					X	X (C4 and C6)	C10, 16, etc	X			
Predose on C1D1, C2D1, C4D1, C6D1 and every sixth cycle sta1ting C10(ie, C1OD1, C16D1, etc). If AE possibly related to ADA occurs, additional samples for ADA and PK should be collected if not scheduled.
 
See Section 8.7.

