3.2.3. Pharmacokinetic Endpoints

- Pre- and post-dose concentrations of elranatamab.

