6.4. Other Secondary Endpoints

6.4.1. Pharmacokinetic/Pharmacodynamics

Pharmacokinetic parameter analyses will be based on the PK Analysis Set. No PK parameter is reported.

A listing of elranatamab concentrations by study visit and timepoint will be generated.

Summary statistics will be provided for pre-dose and post-dose elranatamab concentrations at scheduled visits and nominal timepoints. Values below the limit of quantitation will be treated as zero in the descriptive statistics calculations. For additional details on handling missing and BLQ values, please refer to [Section 5.3.1](#). The summary table will include the number of participants, number of samples with BLQ values, mean, standard deviation, percent coefficient of variation (%CV), median, minimum, maximum, geometric mean, and geometric %CV. For this summary, samples that meet the following conditions will be included:

- For pre-dose samples, have the sample collected before the next dose administration.
- For the 24-hour and 48-hour post-dose samples, have the sample collected within $\pm 25\%$ of the nominal scheduled time.
- At least 2 consecutive planned doses were administered without interruption or reduction prior to trough sample collection.
 - Ex. C1D8 predose is included in the summary if C1D1 and C1D4 were administered as planned (ie, 4 and 20 mg, respectively);
 - Ex. C1D15 predose is included in the summary if C1D4 and C1D8 were administered as planned (ie, 20 and 76 mg, respectively).

Box and Whiskers plots of elranatamab trough concentrations after multiple doses for participants from the PK Analysis Set who meet the conditions stated above will be presented by study visit. The Box and Whiskers plots will be overlaid with geometric means.

In addition, the PK data from this study may be combined with PK data from other studies to develop a population PK model. The correlation between elranatamab exposure parameters and pharmacodynamic biomarker, efficacy and/or safety outcomes will be explored if data allow. Details of these modeling analyses are not within the scope of this SAP and will be described in a separate population PK and exposure response analysis plan.

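### SAP 6.4.1 sets a two-dose condition that the scheduled C1D4 predose sample cannot meet, and sets no dose condition for postdose samples, which leaves a gap at C2D1 24 h in Part 2

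*SAP*

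**What the plan says.** SAP 3.2.3 lists the pharmacokinetic endpoint, which is secondary: "Pre- and post-dose concentrations of elranatamab". SAP 6.4.1 promises summary statistics at scheduled visits and nominal timepoints, then restricts them: "For this summary, samples that meet the following conditions will be included". There are three conditions:

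- A predose sample must be taken before the next dose.
- For postdose samples there is a time window only: "For the 24-hour and 48-hour post-dose samples, have the sample collected within" ±25% of nominal time.
- For troughs: "At least 2 consecutive planned doses were administered without interruption or reduction prior to trough sample collection".

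The SAP does not define a trough. Its two illustrations of the third condition are both predose samples: "C1D8 predose is included in the summary if C1D1 and C1D4 were administered as planned (ie, 4 and 20 mg, respectively") and "C1D15 predose is included in the summary if C1D4 and C1D8 were administered as planned (ie, 20 and 76 mg, respectively"). The box plots of troughs use the same conditions.

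The Part 1 schedule asks for PK samples as "Predose and 24 hon C1D4", and the Part 2 schedule as "Predose and 24 hon C1D4 and C2D1" (the run-together letters come from text conversion; read 24 h on). Protocol 9.3.3.3 plans descriptive statistics of predose and postdose concentrations by cohort, visit and timepoint, and mentions no two-dose restriction.

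**The concern.** The dose condition is missing or unworkable at two scheduled timepoints.

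At C1D4 predose a participant has had one dose, so a two-dose requirement cannot be satisfied however well the schedule was followed. This is the scheduled sample of the concentration a participant carries into the second step-up dose.

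At C2D1 24 h in Part 2 nothing ties the sample to the dose given. That visit is the first at which 116 mg or 152 mg is planned, and the protocol allows escalation only after two 76 mg doses. A participant who has not had them may receive 76 mg at that visit, and the result would still be labelled and summarised as C2D1 24 h for the higher-dose cohort.

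What is at stake is whether two cells of a descriptive secondary-endpoint table can be filled and interpreted.

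**Working it through.** **Step 1: inputs.** Protocol 4.1 gives the Cycle 1 doses: 4 mg on C1D1, 20 mg on C1D4, and 76 mg on C1D8, C1D15 and C1D22. SAP 6.4.1 requires at least 2 planned doses before a trough.

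**Step 2: reproduce the SAP's examples, then apply the same count elsewhere.**

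| Predose sample | Planned doses before it | Last two (mg) | At least 2? |
|---|---|---|---|
| C1D4 | 1 | 4 only | No |
| C1D8 | 2 | 4, 20 | Yes (matches the SAP) |
| C1D15 | 3 | 20, 76 | Yes (matches the SAP) |
| C2D1 | 5 | 76, 76 | Yes |

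Both examples reproduce. C1D4 fails because 1 < 2. A delayed C1D4 does not help: under Protocol 6.5.1.2 treatment may restart at the planned C1D4 dose, so there is still one prior dose. On this reading the failure applies to every participant.

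**Step 3: who can be on 76 mg at C2D1 in Part 2.** Three 76 mg doses are planned before C2D1. If k of them are missed, 3 − k are received. Escalation needs 3 − k ≥ 2 (Protocol 4.1 and 6.5.1.2), so k = 0 or 1 permits it and k = 2 or 3 does not. Missed doses are not made up (Protocol 6.5.1.2).

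**Step 4: apply the inclusion conditions to such a participant.**

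- *C2D1 predose.* The last two planned doses are C1D15 and C1D22. With k ≥ 2, at most one of the three 76 mg doses was given, so C1D15 and C1D22 cannot both have been given. Taking the two most recent doses, as the SAP's examples do, the sample is excluded.
- *C2D1 24 h.* The only test is time: 24 × 0.75 = 18 h to 24 × 1.25 = 30 h. A sample in that range is included whatever dose preceded it. SAP 5.2.11 groups by the visit label on the CRF.

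So the same visit can lose the predose value and keep the 24 h value for the same participant. The two cells would then describe different sets of participants, and the second could mix doses.

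**Step 5: where mixing can occur.** At C1D1 and C1D4 the planned doses are fixed at 4 mg and 20 mg for everyone, so mixing there would need a dosing error. The Part 1 schedule has no C2D1 24 h sample. Within a cohort, the gap is therefore realistic only at C2D1 24 h in Part 2.

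**The case against.** The strongest reply is that the C1D4 exclusion depends on treating predose as trough. SAP 6.4.1 has a separate condition for predose samples, and it describes the plotted troughs as following multiple doses. The literal reading would also reject C1D1 predose, which has no prior dose and is plainly a baseline, so the authors may never have meant the rule for C1D4. This stands as a point about intent. It does not settle the text: both examples call predose samples troughs, and no exception is written. If C1D4 predose is not a trough, it has no check that 4 mg was given as planned. Either way a sentence is needed.

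A reader might infer that the evaluation of exposure and CRS is compromised. The documents do not support that. The C1D1 24 h and 48 h samples are outside the two-dose rule, and Protocol 9.3.3.3 bases its planned CRS correlation on Cmax-24 after the 4 mg dose. Every concentration is still listed. The C1D4 window of −1/+3 days puts the second dose on Day 3 to Day 7, so the 48 h sample approximates the carried-in concentration for the earliest of these, though not for the later ones.

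A reader might also want a percentage dilution at C2D1. None can be derived. Protocol 4.1 reports 7 DLT-evaluable of 12 treated at dose level 1 and 7 of 11 at dose level 2. The remaining 5 and 4 do not give the share on 76 mg at C2D1, because the reasons are not stated and the DLT period runs from the first higher dose, whenever that was. Any dose-proportional calculation of the rise over predose would also describe a statistic that the SAP does not report.

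Other limits on the postdose gap are fair. At least two of three 76 mg doses must be missed. The 24 h sample is not required in Part 2B if hospitalisation is waived. SAP 5.2 reports Part 2A dose level 1 separately from the RP2D group, so 116 mg and 152 mg pool only in overall columns. SAP 5.3.1 lets the clinical pharmacologist set anomalous values to missing, but that is discretionary and not a dose rule.

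**Conclusion.** The point holds in a limited form and is minor. Read literally, and taking predose as trough as the SAP's examples do, the C1D4 predose cell is empty for all participants, against the by-visit summaries in Protocol 9.3.3.3. Separately, the missing dose condition for postdose samples lets a C2D1 24 h value after 76 mg enter a Part 2 cohort's 116 mg or 152 mg summary while the matching predose value is excluded. How often this happened is not known from the documents, so its size is left unstated. Only descriptive tables, and the trough plots that share the conditions, are affected. The primary endpoint, the listings, the C1D1 postdose samples and the Cmax-24 versus CRS analysis are not.

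**What to change.** Amend two phrases in SAP 6.4.1.

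1. Trough condition: 'For C1D4 predose, the C1D1 dose was given as planned; for every later predose sample, the existing two-dose requirement applies.'
2. Postdose condition, added after the time window: 'and the dose preceding the sample was the one planned for that visit; otherwise the sample is summarised by the dose actually received.'

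Inclusion at C1D8 and later predose visits does not change. The edits use dosing records already collected and alter no dosing rule. The cost is that a few C2D1 24 h samples may be removed from the cohort summary or re-labelled, which slightly reduces numbers in that cell.

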6.4.2. Immunogenicity

Immunogenicity data will be analyzed in the Immunogenicity Analysis Set.

The percentage of participants with positive ADA will be summarized. Listings and summary tabulations of the ADA data at baseline and post-baseline will be generated. Samples may also be analyzed for the presence of neutralizing antibodies (NAb), and any data will be similarly summarized. For participants with positive ADA or NAb, the magnitude (titer), time of onset, and duration of ADA or NAb response will also be described, if data permit.

The potential impact of immunogenicity on PK and clinical response including pharmacodynamic markers, safety/tolerability and efficacy will be explored, if warranted by the data. This analysis may be reported separately from the CSR.

CCI [REDACTED]
[REDACTED]
[REDACTED]
[REDACTED]
[REDACTED]
[REDACTED]
[REDACTED]
[REDACTED]
[REDACTED]
[REDACTED]
[REDACTED]
[REDACTED]
[REDACTED]
[REDACTED]

CCI

[REDACTED]

[REDACTED]

[REDACTED]

[REDACTED]

[REDACTED]

[REDACTED]

[REDACTED]

[REDACTED]

[REDACTED]

[REDACTED]

[REDACTED]

[REDACTED]

[REDACTED]

6.6. Subset Analyses

All the subset analyses will be exploratory; no adjustment for multiplicity will be performed. Analyses will only be performed if there is sufficient sample size. The determination of whether or not there is sufficient sample size will be defined after enrollment is complete and prior to database lock. As a general rule, subset analysis will only be performed if there are ≥ 10 participants overall within the defined subset. Deviations from these analyses will be described in the clinical study report.

The following subgroup analyses will be performed for the primary endpoint of Grade ≥ 2 CRS rate:

- Age (<65 vs ≥ 65 ; <75 vs ≥ 75);
- Sex (Male vs Female);
- Race (White vs Black/African American vs Asian vs Others);
- ADA status (positive vs negative);

ADA positive participants are those with treatment-emergent ADA, ie, ADA levels are either a) induced or b) boosted with treatment. Those participants with pre-existing ADA at baseline will be classified as ADA ever positive if their ADA levels are boosted after receiving study intervention.

- Organ function at baseline;
 - Liver function: normal (AST and total bilirubin \leq ULN) vs impaired (AST or total bilirubin $>$ ULN);
 - Renal function: normal (CrCl ≥ 90 mL/min) vs mild (CrCl 60 - 89 mL/min) vs moderate (CrCl 30 - 59 mL/min).

The following subset analyses may be performed for ORR as determined by investigator:

- Baseline cytogenetics (high risk = Yes vs. No);
- Number of prior therapies (≤ 4 , >4);
- Prior BCMA-target agent (Yes vs. No);
- EMD at baseline (Yes vs. No).

Grade ≥ 2 CRS rate and ORR in subsets will be presented in a forest plot. Additional subset analysis might also be performed if data permits.

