#### 1.3.1. Part 1 Schedule of Assessments

**Table 1. Schedule of Assessments: Part 1**

Visit Identifier	Screening	Treatment Period Cycle 1					Treatment Period (each 28 Day Cycle)		EOT Visit	FU Visit	LTFU Q12W	Notes/Protocol Section
		Day1	Day4	Day8	Day15	Day22	Cycles 2-6 Day1	Cycle7 Onwards Day1				
Visit Window	Day-28 to Day-1	-	-1/+3 D	-1/+3 D	±3D	±3D	±3D	±3D	1-4 D post- final dose	28 to 35 days post- final dose	±14D	
Info/med consent	X											See Section 10.1.3.
Eligibility criteria	X											See Section 5.1 and Section 5.2.
Register with IRT	X											See Section 6.3.1.
Enrollment in IRT		X										See Section 6.3.1
Demography/ medical history	X											See Section 8.2.1.
Disease characteristics/ treatment history	X											See Section 8.2.1.
Clinical Procedures/Assessments - Note: From the treatment period, all assessments must be done within 72 hours prior to dosing, except for disease assessments which are to be done every 28 days from CID1												
Physical exam	X	X	X				X	X*	X	X		

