### 2.3.1. Risk Assessment

Potential Risk of Clinical Significance	Summary of Data/Rationale for Risk	Mitigation Strategy
Study Intervention: Elranatamab monotherapy		

CRS
	
A known toxicity of therapeutics that function by activation of immune effector cells.
 
Circulating cytokines are elevated after IV or SC administration of elranatamab. CRS signs and symptoms are expected mainly after the first and second dose and occasionally after the third or later doses of elranatamab.
 
In the present study, elranatamab dose will be increased to > 76 mg starting from Cycle 2 either with longer dosing intervals in Part 2A DLI, Part 2A DL2, and Part 2B CCI [REDACTED]
 
For Part 2, the planned regimen would result in up to 2-fold higher Cmax on Cycle 2 Day 1 (152 mg Q2W) compared to 76 mg QW. Higher Cmax during the first 24 hours of the first
	
Participants will be hospitalized for at least 2 days after the CID1 dose and at least 1 day after the CID4 dose for safety surveillance (Part 1, Part 2). Hospitalization from CID1 to CID5 may be considered. Since CRS events occurred after the first (predominantly within the first 2 days) and second dose of eh-anatamab, the planned 2-day hospitalization after the first dose allows for the detection of initial CRS signs and symptoms and enables timely management of these events according to the ASTCT management guidelines. The 1-day hospitalization on CID4 is considered adequate given the anticipated lower incidence and grade CRS after the second step-up dose of 20 mg.
 
For Part 2A, participants will be hospitalized for at least 1 day also on C2D1. For Part 2B and Part 2C, hospitalization on C2D1 may not be required depending on CRS profile observed in Part 2A. For participants enrolled in Part 1 who would switch to the RP2D Q4W, optional hospitalization may be considered on the day of RP2D administration depending on CRS profile observed in Part 2A and Part 2B.
 
The 2 step-up priming doses schema is expected to mitigate the rate and severity of CRS, which is mainly expected after the first 1 to 2 doses.
 
To further mitigate the CRS risk, premedications will be administered prior to the first 3 doses on CID1, CID4 and CID8 (see Section 6.8.I). No premedications will be administered on C2D1 for Part 2 as the risk of CRS after repeated eh-anatamab administration, even with a higher eh-anatamab dose, is considered low.
 
Guidance for monitoring, grading, and management of CRS per ASTCT criteria and guidelines is included in Appendix 12.
 
Dose modification/discontinuation in the setting of Grade 2 AEs (including CRS) is described in Section 6.5.
 
This study will include only participants who are likely to tolerate potential events of CRS by excluding participants who are particularly susceptible to complications of CRS, including those with impaired cardiac function or clinically significant CV disease (see Section 5.1 and Section 5.2).
 
Criteria for temporary study hold based on Grade 3 CRS events are described in Section 9.4.1.

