#### 4.3.1. Justification for the 2 Step-up Priming Doses Regimen

In the SC cohorts from Study C1071001, only 2 out of 50 participants experienced CRS after the second dose and no CRS events were observed after the third or later doses. The rate of Grade 1 and 2 CRS events in participants receiving dose levels 600 µg/kg (which is the body weight dosing equivalent of 44 mg) is 62.5% and 37.5%, respectively, according to ASTCT grading. The maximum severity of CRS was consistently observed after the first dose including participants in the priming cohorts who received a higher dose on C1D8 indicating that CRS is associated mostly with the initial exposure (ie, the first dose). A logistic regression analysis that included data from both IV (n =23) and SC cohorts (n = 43) from Study C1071001 shows an association between eh-anatamab Cmax within 24 hours post first dose (Cmax-24h) and probability of CRS of All Grade and Grade 2 and higher (according to ASTCT criteria, Figure 1)

Priming dose approaches are commonly applied for T cell engager bispecific modalities to initially sensitize the immune system at lower doses to reduce rate and grade of CRS.[31-34]

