5.2.5. Definition of Cycle and Cycle Day

Cycle start and end dates are derived per participant. The definition for each cycle is driven by the study intervention elranatamab. Elranatamab is administered in a 28-day cycle.

- For Cycle 1, the actual cycle start date is the date each participant receives the first non-zero study intervention;
- For all other cycles, the actual cycle start date for each participant is the earliest start date of dosing in the Cycle X Day 1 visit CRF exposure page;
- For all but the last cycle:
 - Actual cycle stop date is calculated as the start date of the next cycle minus 1 day;
 - Actual cycle duration is calculated from Day 1 of a cycle to the day prior to Day 1 of the next cycle, as follows:

$$\text{Actual Cycle Duration (weeks)} = (\text{cycle stop date} - \text{cycle start date} + 1)/7$$

- For the last cycle, actual cycle duration is the planned cycle duration and actual cycle stop date is calculated as actual cycle start date + 28 – 1 day.

The cycle day will be calculated as:

$$\text{Cycle day} = \text{Date of the assessment/event} - \text{cycle start date} + 1.$$

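### SAP 6.6 subgroups Cycle 1 Grade ≥2 CRS by treatment-emergent ADA, which routine sampling first detects at C2D1, well after the doses at which CRS is mainly expected

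*SAP*

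**What the plan says.** SAP 6.6 names the subgroups for the Cycle 1 Grade ≥2 CRS rate: age, sex, race, ADA status and organ function at baseline. ADA status has two levels, positive and negative. The definition reads: "ADA positive participants are those with treatment-emergent ADA, ie, ADA levels are either a) induced or b) boosted with treatment". A participant who already has ADA at baseline "will be classified as ADA ever positive if their ADA levels are boosted after receiving study intervention". Neither sentence sets a date by which the change must be seen. The results go into a forest plot with the other subgroups. SAP 6.6 also states: "All the subset analyses will be exploratory; no adjustment for multiplicity will be performed". As a general rule, a subset needs at least 10 participants to be analysed.

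The schedules of assessments for Part 1 and Part 2 (Protocol Tables 1 and 2) give the same ADA sampling: predose at C1D1, C2D1, C4D1 and C6D1, then every sixth cycle from C10, plus the end-of-treatment visit. Extra samples are taken if an adverse event possibly related to ADA occurs.

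On the end of Cycle 1, SAP 5.2.5 says: "Actual cycle stop date is calculated as the start date of the next cycle minus 1 day". On the timing of CRS, Protocol 2.3.1 says: "CRS signs and symptoms are expected mainly after the first and second dose and occasionally after the third or later doses of elranatamab". For the SC cohorts of Study C1071001, Protocol 4.3.1 reports that "only 2 out of 50 participants experienced CRS after the second dose and no CRS events were observed after the third or later doses".

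**The concern.** A subgroup factor is normally fixed before the outcome, so that a difference between its levels can be read as a difference between kinds of participant. Age, sex, race and baseline organ function meet that condition. Treatment-emergent ADA does not. It develops after dosing begins, and routine sampling first looks for it about four weeks later, when most CRS should already have occurred.

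If the forest plot showed more or less CRS among ADA-positive participants, a reader would naturally take ADA as a predictor or modifier of CRS. The sampling cannot support that. The status also depends on how long a participant stays on treatment, since more cycles mean more chances to turn positive. Post-dose samples before C2D1 exist only where an adverse event or stopping treatment prompted them, so their timing may itself depend on toxicity. Nothing in SAP 6.6 warns that this row differs from its neighbours.

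**Working it through.** The documents state no figure for this point, so the check compares days.

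**Inputs.** Dose 1 is Day 1, dose 2 is Day 4 and the first full dose is Day 8 (Protocol 4.1). Cycles last 28 days (SAP 5.2.5). The visit window is −1/+3 days for C1D4 and ±3 days for C2D1 (Protocol Tables 1 and 2).

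**Scheduled ADA days.** Day 1 of cycle x falls on 28 × (x − 1) + 1:
- C2D1: 28 × 1 + 1 = Day 29
- C4D1: 28 × 3 + 1 = Day 85
- C6D1: 28 × 5 + 1 = Day 141
- C10D1: 28 × 9 + 1 = Day 253

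The C1D1 predose sample is the baseline and cannot show induced or boosted ADA. C2D1 is therefore the first scheduled sample that can, for those continuing treatment.

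**Nominal gaps to the C2D1 sample.** From dose 1: 29 − 1 = 28 days. From dose 2: 29 − 4 = 25 days. From the first full dose: 29 − 8 = 21 days.

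**Gap from dose 2 to the C2D1 dose with both doses inside their windows.** Shortest: 26 − 7 = 19 days. Longest: 32 − 3 = 29 days.

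**Allowing for early collection.** A note in Table 1 says "all assessments must be done within 72 hours prior to dosing". If it covers ADA, the sample could be drawn on Day 26 − 3 = Day 23, and the shortest gap would be 23 − 7 = 16 days. This figure has two conditions. The note sits under the clinical procedures heading, whereas ADA is listed under pharmacokinetics and immunogenicity. Dose 2 must also fall inside its window, and Protocol 6.5.1.2 allows it to be given later.

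**Position relative to the endpoint.** By SAP 5.2.5, any Cycle 1 event precedes the C2D1 dose. A sample taken on the C2D1 dosing day lies just outside Cycle 1; one taken up to 72 hours earlier would lie in its last 3 days. In the earlier study, which used other starting doses, CRS after dose 2 was 2/50 = 4.0%, with none after dose 3 or later.

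**When the row would appear.** At the planned total, 10/76 = 13.2% would have to be ADA-positive. The documents give no ADA rate. Actual enrolment also departed from plan: Protocol 4.1 reports 12 and 11 participants at the two Part 2A dose levels and says Part 2C will not be explored.

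**Definitions side by side.** Protocol 9.3.3.4 counts participants with at least one positive post-dose ADA result. SAP 6.4.2 says only positive ADA. SAP 6.6 requires induction or boosting. A participant with pre-existing ADA that persists without boosting is positive under Protocol 9.3.3.4 but not under SAP 6.6.

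**The case against.** The strongest reply is that no wrong inference is planned. The subset analyses are labelled exploratory, and no test, decision or causal claim hangs on the ADA row. Exploring immunogenicity against safety is a stated aim in Protocol 9.3.3.4 and SAP 6.4.2. Much of the timing information is already planned: SAP 6.4.2 describes ADA onset and duration if data permit, and SAP 6.8.1.1 summarises CRS onset and timing relative to dose. A careful reader of the study report could reconstruct the order, and a footnote might serve.

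This limits the weight of the point but does not remove it. The exploratory label does not change the time order, and the plan puts this row beside baseline factors without distinguishing it.

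Several stronger readings are tempting but not supported:
- *Participants without a post-dose ADA sample are counted as negative.* SAP 6.6 does not say so. SAP 5.2.13 defaults to a separate missing category and SAP 5.3 to no imputation. The gap is only that SAP 6.6 names two levels.
- *The ever-positive wording governs everyone.* It is used only for participants with pre-existing ADA; the induced category simply has no time limit.
- *Positive ADA is left undefined.* Protocol 9.3.3.4 describes it; the descriptions differ between sections.
- *All ADA information postdates Cycle 1.* Event-prompted and end-of-treatment samples can come earlier, and early collection of the C2D1 sample could fall inside Cycle 1.

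**Conclusion.** The point holds and is minor. The primary endpoint is subgrouped by a factor that, for participants continuing treatment, is first routinely detectable 25 days after dose 2 on the nominal schedule, and that can change for months afterwards while the Cycle 1 CRS result stays fixed. The row cannot be interpreted like the baseline factors around it.

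This rests on the published ADA schedule and on the protocol's expectation about CRS timing. A reader might infer that ADA arises after CRS, or that the subgroup result is biased in a known direction. The documents support neither: they fix when ADA is looked for, not when it develops, and direction and size are unknown and may be nil. Nor does the point reach the primary estimate, the futility rule or the limit of 20 events in 76. The effect is confined to one exploratory row that may not be shown at all.

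**What to change.** In SAP 6.6, remove treatment-emergent ADA from the primary-endpoint subgroups and the forest plot, or replace it with baseline (C1D1 predose) ADA if the 10-participant rule is met. Baseline ADA is drawn before dosing and can be read like the other factors.

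Keep the ADA–CRS relation as a descriptive table under SAP 6.4.2, showing ADA onset and CRS dates. Participants without a post-dose ADA sample should appear as missing, consistent with SAP 5.2.13. State that the table belongs in the CSR, because SAP 6.4.2 otherwise lets its impact analysis be reported separately. Align the ADA-positive definition across SAP 6.4.2, SAP 6.6 and Protocol 9.3.3.4.

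The cost is one list entry removed or replaced, one descriptive table and a few sentences, with no new data. The downside is that the treatment-emergent ADA row is lost from the forest plot.
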